**REVISION HISTORY**

*This Revision History table is provided for the benefit of study team version control. If this table will not be useful please delete it.*

Revision #	Version Date	Summary of Changes	Consent Change?

## STUDY INFORMATION

### 1.0 Study Summary\*

Study Title	An Investigation of the Diabetes Link Discord Platform
Study Design	Single site, pilot, longitudinal
Primary Objective	To examine the feasibility and acceptability of the Diabetes Link's online social platform Discord among youth with diabetes as it relates to peer support, diabetes management, and usability.
Secondary Objective	To examine the efficacy/magnitude of the effect of the Discord group on treatment adherence among youth with diabetes.
Research Intervention(s)	Participants will join the Children's Mercy Discord group led by the nonprofit Diabetes Link. Participants will participate in live video gatherings, as well as posted chats/prompts, and will answer a few qualitative questions at the end of their participation. Discord user metrics--both quantitative and qualitative (deidentified transcripts/audio recordings)--and health record metrics will be analyzed in addition to the end survey.
IND/IDE #	N/A
Study Population	T1D patients in 11 th and 12 th grade (ages 16-19) who have access to a smartphone/laptop and speak English
Sample Size	Sample size for app use: 20 11 th /12 th graders
Study Duration for Individual Participants	Users will use Discord for 3 months.
Study Specific Abbreviations/Definitions	DL = Diabetes Link Nonprofit Organization T1D= type one diabetes T2D= type two diabetes Children's Mercy Hospital Kansas City (CMH) Mobile Application (app or apps) Children's Mercy- Kansas City (CMKC)

### 2.0 Objectives\*

#### 2.1 Purpose, specific aims or objectives:

Aim 1: To examine the feasibility and acceptability of the Diabetes Link's online social platform Discord among youth with diabetes as it relates to peer support, diabetes management, and usability.

Aim 2: To examine the efficacy/magnitude of the effect of the Happy Bob app on treatment adherence among youth with diabetes.

## **2.2 Hypothesis:**

Aim 1, Hypothesis: The intervention will be considered feasible, and patients will be satisfied with the Discord peer group, as assessed with enrollment rate, retention and refusal rates, attrition rate, usage, as well as perceptions of the format, organization, and content of the app, perceived impact on disease/treatment management, and satisfaction with the app.

Aim 2, Hypothesis 1: Participants will demonstrate increased treatment engagement while participating in the Discord platform.

Aim 2, Hypothesis 2: Participants who increase treatment engagement as a result of this intervention will experience better diabetes-related health outcomes.

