## **3.0 Background\***

According to the CDC's National Diabetes Statistics Report, 2020, approximately 187,000 children and adolescents in the United States are living with type 1 diabetes (T1D). Managing T1D among youth can be challenging and time consuming. It requires adherence to routine blood glucose monitoring, insulin administration as well as close attention to balancing physical activity and diet. Effective management of T1D in youth is key to good glycemic control. Attaining good control early in the course of T1D is important for reducing the risk of T1D-related complications (e.g. metabolic memory; Chemtob et al., 2011; Ceriello, 2012; Giordano et al., 2011; Pop-Busي et al., 2010 Silverstein et al., 2005;). Some children and families excel when faced with the challenges of T1D, while others struggle with their disease, as evidenced by declining glycemic control (Helgeson et al., 2010; Kia-Keating et al., 2011; Rausch et al., 2012).

Improved engagement with treatment options (e.g. standard of care visits, **peer mentoring**, direct to consumer telehealth, digital therapeutics, etc.) will result in better glycemic control and will ultimately help reduce the risk of acute and chronic diabetes related complications. Furthermore, *a review by Oser and colleagues found that “diabetes online communities have grown” and “enabled communities of peers to both seek and receive support for living with diabetes, providing an important supplement to what is provided in healthcare settings” (2020). We would like to quantitatively and qualitatively evaluate the impact of these online communities.*

Our preliminary data—from focus groups, online events hosted by the Diabetes clinic, the clinic intake form, and ADA camp participation—highlights the desire among teens with T1 to connect with T1 peers.

A Canadian internet-based study found that 65% of youth aged 14 to 24 years with T1D reported stigma related to the disease. In response, a Virtual Peer Network (VPN) was built to provide a forum for peer

relatedness and social support. The VPN examined the proportions of different types of exchanges and delineated the topic of importance to members. The study's findings support the building of internet-based peer communities for T1D and other chronic conditions as they constitute a valuable resource for chronic disease management. (Wu et al. 2023)

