The Canadian study found that "the ratio of comments, reactions, and views to posts were 3.6 to 1, 5.3 to 1, and 57 to 1, respectively," and that involvement increased with time. Comments were coded, and over 50% fit into social support categories (informational support, self-esteem support, etc). And 10 themes emerged: (1) intersections of T1D and life (school, work, travel, driving); (2) relationships between glucose levels and habits (alcohol, etc); (3) T1D and social relationships; (4) stories about diagnosis, milestones, and identity; (5) self-management; (6) meeting and interacting with others with T1D; (7) experience with healthcare providers/health system; (8) T1D and society (policy issues, insurance); (9) technology, supplies, and materials; (10) T1D and public sphere (advocacy). This study provides support for the online content and metrics we will incorporate into our study, and it also highlights an area in which we can add value. This Canadian study did not query participants about the value the social network provided them, and this is something we certainly intend to do. Social support/confidence/etc is a contributor to diabetes management, and thus diabetes outcomes, and so we want to examine the value that social support brings, and also the effect that that value then brings to management and outcomes.

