#### **4.0 Study Endpoints N/A**

#### **5.0 Study Design\***

##### **4.1 Study Design: *pilot, single site, longitudinal***

#### **6.0 Study Interventions\***

##### **5.1 Description: *Describe the study intervention and/or experimental manipulation that is being evaluated.***

##### **5.2 Behavioral Intervention: *If this study involves a behavioral intervention, describe the intervention in detail. Be sure to address whether the intervention is experimental or considered to be an accepted standard.***

The nonprofit organization Diabetes Link hosts an online Discord peer support server for young adults with Type 1 Diabetes. On the server, there are different channels for different topics (relationships, mental health, nutrition, etc). The Link has a library of resources called the [Resource Hub](#) (articles, worksheets, videos, etc) on various diabetes-related topics. The Diabetes Link has staff who monitor the server, host live online events, post conversation starters, and more to foster interaction among members. For this study, Diabetes Link will create a special server just for Children's Mercy study participants for at least 3 months. The organization's employees will not enroll Human Subjects or obtain the informed consent of any Human Subject for participation in the Research. A live video session will be held at the start to go over server etiquette, introductions, etc. Over the course of the 3 months, about 6 live video events will be held, hosted by Diabetes Link staff, allowing participants to interact. Events could be anything from watching a movie together, to informal chats, to question and answer sessions, etc. The DL staff will also make weekly posts for participants to respond to.

Employing the strategy of behavioral economics, up to 6 raffles will be held throughout the trial. Participants can earn a raffle entry for every 1 live event attended and/or for every 3 posts made. After 3 months of Discord use, participants will be asked a few survey questions about their experience.

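### Hypothesis 2 and the secondary efficacy objective attribute change to Discord, which the one-cohort design shown can describe but cannot attribute

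*Protocol*

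**What the plan says.** Protocol Section 2.2, Aim 2, Hypothesis 2: "Participants who increase treatment engagement as a result of this intervention will experience better diabetes-related health outcomes". Section 1.0 gives the secondary objective as "To examine the efficacy/magnitude of the effect of the Discord group on treatment adherence among youth with diabetes". Aim 2 in Section 2.1 has the same form but a different product: "To examine the efficacy/magnitude of the effect of the Happy Bob app on treatment adherence among youth with diabetes".

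Hypothesis 1 is worded in terms of time, not cause: "Participants will demonstrate increased treatment engagement while participating in the Discord platform". The objective and Aim 2 speak of adherence; both Aim 2 hypotheses speak of engagement.

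On design, Sections 1.0 and 5.0 describe a longitudinal pilot at a single site. Section 1.0 gives "Sample size for app use: 20". The enrolment table in Section 8.0 has one enrolled group of 20 beside a prescreening count of 65. Section 6.0 places all participants on one server: "For this study, Diabetes Link will create a special server just for" this study's participants, for at least 3 months. None of these sections names a control group, randomisation or a historical comparator.

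**The concern.** The secondary objective and Hypothesis 2 make causal statements. The design shown supports descriptive ones. There are two separate difficulties.

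- **Attribution.** With everyone exposed and no comparator, a change over 3 months mixes any effect of Discord with background drift, regression to the mean and concurrent care.
- **An unobservable subgroup.** Hypothesis 2 is about people whose rise in engagement was caused by the intervention. The data can show who rose, but not whose rise Discord caused.

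At stake is how the secondary results are read. A before-after change could be reported as efficacy. An association between engagement and outcome could be reported as a health benefit of Discord.

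**Working it through.** **The plan's own figure.** The sample size of 20 comes with no effect size, SD, error rate or power in the text at hand, so there is nothing to reproduce. A feasibility pilot does not need such a derivation. What follows tests the claims against the design.

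**Step 1: attribution.** Write each participant's change as an effect of Discord plus the change that would have happened anyway. The cohort mean then estimates:

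mean change = (mean Discord effect) + (mean background change)

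There is one observed quantity and two unknowns. A larger sample narrows the interval around the sum but does not separate the two parts.

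As an illustration, suppose Discord has no effect, background drift is 0.2, 0.3 or 0.5 SD of the change, and a two-sided 5% paired t-test is used. The drift values and the test are my assumptions; the text shown states neither. The noncentrality is drift × √20, that is 0.89, 1.34 or 2.24. The chance of a favourable significant result is then 13%, 25% or 56%.

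**Step 2: the subgroup.** For one participant, let D1 be the change in engagement with Discord and D0 the change without it. Hypothesis 2 selects people with D1 above zero and D1 greater than D0. Only D1 is ever seen. A control group would show D0 in other people, which identifies the average difference but not the members of the subgroup.

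Risers also occur with no effect at all. If changes are equally likely to be up or down (assumed), the number of risers follows a Binomial(20, 0.5) distribution. Its mean is 20 × 0.5 = 10, and its 95% range is 6 to 14.

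**Step 3: what 20 participants can give.**

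- Mean within-person change, 95% half-width in SDs of the change: t(0.975, 19)/√20 = 2.093/4.472 = 0.468, about 0.47 SD.
- The same with 16 completers (assumed, to allow for dropout): t(0.975, 15)/√16 = 2.131/4 = 0.53 SD.
- Association across all 20, limits around an observed correlation of zero: ± tanh(1.96/√17) = about ±0.44.

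These are imprecise but legitimate pilot estimates, and none of them needs causal wording.

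**The case against.** **Sections not shown.** Sections 10 to 30, including Data Collection and Statistical Analysis, are not in the text at hand. They might define a comparator or a pre-enrolment series. This stands as a limit on Step 1, and the absence of a comparator remains an inference. It does not touch Step 2, because no analysis plan can make individual causation observable.

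**It is a pilot.** The objective's reference to magnitude can be read as effect-size estimation. That is a fair reading of the intent. It leaves the word efficacy, and the attribution inside Hypothesis 2, saying more than the design does. The remark in Section 3.0 about "the effect that that value then brings to management and outcomes" is motivation, and I do not count it as a claim.

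Two stronger readings are tempting, and the documents do not support them.

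- **A reader might infer that Hypothesis 2 is bound to look confirmed.** Assume no Discord effect, and correlations of 0.1, 0.3 or 0.5 between change in engagement and change in outcome. Risers then beat non-risers in 64%, 86% or 97% of simulated studies. But that counts any positive difference; the difference is significant in only 5%, 17% or 44%. The protocol text shown does not state a riser versus non-riser test. The correlation across all participants, which is what I recommend, would be positive even more often (67%, 91% or 99%). These figures show that an assumed association gets found. They do not show a fault that rewording removes.
- **A reader might infer that use of the Discord server would itself count as engagement**, since Section 3.0 lists peer mentoring under "Improved engagement with treatment options". The protocol points the other way. Section 2.2 puts usage under the Aim 1 feasibility hypothesis, Hypothesis 1 treats engagement and participation as different things, and Section 1.0 separates Discord user metrics from health record metrics.

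**Conclusion.** Wrong as written, and minor to moderate in weight. Hypothesis 2 defines its group by a cause that cannot be observed in individuals under any design. The secondary objective and Aim 2 claim efficacy that the one-cohort design shown cannot establish. The first conclusion rests only on the wording of Section 2.2. The second assumes that the sections not at hand define no comparator.

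The missing comparator drives the attribution problem; the sample of 20 adds imprecision, about ±0.47 SD on a mean change with full completion. The primary feasibility and acceptability aim and Hypothesis 1 are unaffected.

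**What to change.** 1. **Section 2.2, Hypothesis 2.** Delete the clause that attributes the rise to the intervention, and drop the subgroup. Suggested wording: *Exploratory: across all participants, change in treatment adherence is associated with change in diabetes-related health outcomes.*
2. **Sections 1.0 and 2.1.** Replace the efficacy wording in both with the same sentence, for example: *To estimate the change in treatment adherence during participation in the Discord group; without a comparator this change cannot be attributed to Discord alone.* If a comparator is defined elsewhere, name it here instead of the caveat.
3. **Section 2.1, Aim 2.** Reconcile the intervention with Section 1.0. It now names the Happy Bob app where Section 1.0 names the Discord group.
4. **Terminology.** Use one term, adherence or engagement, in the objective, Aim 2 and both hypotheses. The suggestions above use adherence; engagement would serve if used throughout.

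The cost is edits to three sections, with no new participants. The downside is a more modest secondary claim. The sponsor should also confirm that a baseline value is available, since an estimate of change needs one.

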## **3.0 Background\***

According to the CDC's National Diabetes Statistics Report, 2020, approximately 187,000 children and adolescents in the United States are living with type 1 diabetes (T1D). Managing T1D among youth can be challenging and time consuming. It requires adherence to routine blood glucose monitoring, insulin administration as well as close attention to balancing physical activity and diet. Effective management of T1D in youth is key to good glycemic control. Attaining good control early in the course of T1D is important for reducing the risk of T1D-related complications (e.g. metabolic memory; Chemtob et al., 2011; Ceriello, 2012; Giordano et al., 2011; Pop-Busي et al., 2010 Silverstein et al., 2005;). Some children and families excel when faced with the challenges of T1D, while others struggle with their disease, as evidenced by declining glycemic control (Helgeson et al., 2010; Kia-Keating et al., 2011; Rausch et al., 2012).

Improved engagement with treatment options (e.g. standard of care visits, **peer mentoring**, direct to consumer telehealth, digital therapeutics, etc.) will result in better glycemic control and will ultimately help reduce the risk of acute and chronic diabetes related complications. Furthermore, *a review by Oser and colleagues found that “diabetes online communities have grown” and “enabled communities of peers to both seek and receive support for living with diabetes, providing an important supplement to what is provided in healthcare settings” (2020). We would like to quantitatively and qualitatively evaluate the impact of these online communities.*

Our preliminary data—from focus groups, online events hosted by the Diabetes clinic, the clinic intake form, and ADA camp participation—highlights the desire among teens with T1 to connect with T1 peers.

A Canadian internet-based study found that 65% of youth aged 14 to 24 years with T1D reported stigma related to the disease. In response, a Virtual Peer Network (VPN) was built to provide a forum for peer

relatedness and social support. The VPN examined the proportions of different types of exchanges and delineated the topic of importance to members. The study's findings support the building of internet-based peer communities for T1D and other chronic conditions as they constitute a valuable resource for chronic disease management. (Wu et al. 2023)

The Canadian study found that "the ratio of comments, reactions, and views to posts were 3.6 to 1, 5.3 to 1, and 57 to 1, respectively," and that involvement increased with time. Comments were coded, and over 50% fit into social support categories (informational support, self-esteem support, etc). And 10 themes emerged: (1) intersections of T1D and life (school, work, travel, driving); (2) relationships between glucose levels and habits (alcohol, etc); (3) T1D and social relationships; (4) stories about diagnosis, milestones, and identity; (5) self-management; (6) meeting and interacting with others with T1D; (7) experience with healthcare providers/health system; (8) T1D and society (policy issues, insurance); (9) technology, supplies, and materials; (10) T1D and public sphere (advocacy). This study provides support for the online content and metrics we will incorporate into our study, and it also highlights an area in which we can add value. This Canadian study did not query participants about the value the social network provided them, and this is something we certainly intend to do. Social support/confidence/etc is a contributor to diabetes management, and thus diabetes outcomes, and so we want to examine the value that social support brings, and also the effect that that value then brings to management and outcomes.

#### **4.0 Study Endpoints N/A**

#### **5.0 Study Design\***

##### **4.1 Study Design: *pilot, single site, longitudinal***

#### **6.0 Study Interventions\***

##### **5.1 Description: *Describe the study intervention and/or experimental manipulation that is being evaluated.***

##### **5.2 Behavioral Intervention: *If this study involves a behavioral intervention, describe the intervention in detail. Be sure to address whether the intervention is experimental or considered to be an accepted standard.***

The nonprofit organization Diabetes Link hosts an online Discord peer support server for young adults with Type 1 Diabetes. On the server, there are different channels for different topics (relationships, mental health, nutrition, etc). The Link has a library of resources called the [Resource Hub](#) (articles, worksheets, videos, etc) on various diabetes-related topics. The Diabetes Link has staff who monitor the server, host live online events, post conversation starters, and more to foster interaction among members. For this study, Diabetes Link will create a special server just for Children's Mercy study participants for at least 3 months. The organization's employees will not enroll Human Subjects or obtain the informed consent of any Human Subject for participation in the Research. A live video session will be held at the start to go over server etiquette, introductions, etc. Over the course of the 3 months, about 6 live video events will be held, hosted by Diabetes Link staff, allowing participants to interact. Events could be anything from watching a movie together, to informal chats, to question and answer sessions, etc. The DL staff will also make weekly posts for participants to respond to.

Employing the strategy of behavioral economics, up to 6 raffles will be held throughout the trial. Participants can earn a raffle entry for every 1 live event attended and/or for every 3 posts made. After 3 months of Discord use, participants will be asked a few survey questions about their experience.

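### Do the two descriptions of the experience survey's timing conflict, so that participants who leave early might not be asked about satisfaction?

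*Protocol*

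**What the plan says.** The survey is mentioned in two places. The Research Intervention(s) row of section 1.0 says participants "will answer a few qualitative questions at the end of their participation", and the same row later refers to this instrument as the survey at the end. Section 5.2, Behavioral Intervention, closes its description of the server, the live events and the raffles with "After 3 months of Discord use, participants will be asked a few survey questions about their experience".

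The planned length of participation is in section 1.0, under Study Duration for Individual Participants: "Users will use Discord for 3 months". Section 5.2 adds that the nonprofit will run a "special server just for Children's Mercy study participants for at least 3 months".

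The use of the answers is set out in section 2.2. The Aim 1 hypothesis judges feasibility "as assessed with enrollment rate, retention and refusal rates, attrition rate, usage", and judges acceptability by perceptions of the format, organization and content together with "perceived impact on disease/treatment management, and satisfaction with the app". The planned size is given in section 1.0: "Sample size for app use: 20".

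**The concern.** The two sentences use different words for the trigger. Section 5.2 can be read as requiring 3 months of actual use before the survey is offered. Section 1.0 can be read as offering it whenever a person's participation ends. For someone who leaves at, say, week 5, the first reading gives no survey and the second gives one at exit.

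That would matter for Aim 1. The hypothesis in section 2.2 lists "retention and refusal rates, attrition rate, usage" among its measures, so some loss is expected, and it also relies on satisfaction. People who drop out of a peer group may like it less than those who stay. If only stayers answered, reported satisfaction could be too high. Server metrics show that someone stopped, but not what that person thought of the group. With 20 participants, a few unasked leavers could change the picture, and answers never requested cannot be recovered at analysis.

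**Working it through.** The question is mainly one of reading, so the statements are set side by side.

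| Item | Place in the protocol | Content |
|---|---|---|
| Survey timing | 1.0, Research Intervention(s) | end of participation |
| Survey timing | 5.2 | after 3 months of Discord use |
| Length of participation | 1.0, Study Duration | 3 months of Discord use |
| Who is asked | 5.2 | participants, with no further condition |

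**Step 1: Do the two times differ?** Put the third row into the first. Participation lasts 3 months of Discord use, so its end falls after 3 months of Discord use. That is the second row. The two sentences give one planned time point.

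**Step 2: Does section 5.2 restrict the survey to those who kept using the server?** The sentence has participants as its subject and names no minimum use, number of posts, attendance or completer status. The same section uses 3 months as a fixed period when it schedules about 6 live events across it. In that setting the phrase marks the close of the period. It takes an added assumption to turn it into an eligibility rule for the survey.

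**Step 3: What is left?** The available text does not say in so many words what happens to someone who withdraws early. A study summary and an intervention description are not where that rule is normally written. The contents list 10.0 Surveys and Psychometric Testing, 12.0 Follow-Up, 25.0 Withdrawal of Participants and 26.0 Data Collection, which are. The text at hand goes from section 9.0 straight to 31.0, so none of these can be read, and nothing can be inferred from their absence.

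**Step 4: Could a size be attached?** Only by assumption. The available text gives no expected attrition, no satisfaction target and no yes/no satisfaction item; section 1.0 describes the questions as qualitative. Suppose such an item existed, with n = 20, L unsurveyed leavers and 2 dissatisfied stayers. Then:

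- satisfaction among stayers = (18 − L)/(20 − L)
- lowest possible share of all enrolled = (18 − L)/20
- highest possible share = 18/20 = 90%

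| L (assumed) | Stayers | Lowest, all 20 | Highest, all 20 |
|---|---|---|---|
| 2 | 16/18 = 89% | 16/20 = 80% | 90% |
| 4 | 14/16 = 88% | 14/20 = 70% | 90% |
| 6 | 12/14 = 86% | 12/20 = 60% | 90% |

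The range for all enrolled widens as L grows, which is the worry. But L, the number dissatisfied and the item itself are all supplied from outside the document. In every row the highest value lies above the stayers' figure, so even the direction of bias depends on what is assumed about leavers. The table shows what would follow if the survey were limited to stayers. It is not evidence that the plan limits it so.

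**The case for a change.** The best case for the concern is that it alleges no omission in the absent sections. It rests on two visible sentences with different triggers, and those should match whatever the rule is. Who receives a survey is data collection, not analysis, so a SAP cannot repair it. Section 5.2 also ties raffle entries to attendance and posts, so continued use is partly rewarded, which is one more reason not to let the survey depend on use. One shared wording would cost little.

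Part of this stands. Surveying only stayers could overstate satisfaction, and identical phrasing in 1.0 and 5.2 would be tidier. But the sentences diverge only if the phrase in 5.2 is taken as a usage threshold, which its text does not state. The raffle argument shows why such a threshold would be unwise, not that there is one.

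Rewording without sight of the withdrawal and survey sections also carries a risk. Timing the survey from the opening of the server, for example, would reach anyone who joined late before they had 3 months of exposure, and the visible text does not say that everyone joins on the first day. Reporting satisfaction among responders alongside a bound for all enrolled is sensible, but that is handling of missing data and commonly left to the SAP.

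**Conclusion.** The concern does not hold. Given the 3-month participation stated in section 1.0, the two sentences name the same time point, and neither excludes early leavers from the survey. No stated rule is shown to give a wrong result for Aim 1, and no size can be assigned to a bias, since every figure needed for one would have to be assumed. Attrition is not hidden either: section 2.2 lists retention, attrition and usage beside satisfaction, so a satisfaction result would be read together with the number who left.

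This rests on reading the phrase in section 5.2 as the close of the planned period, which its context supports. It also rests on not treating sections absent from the text at hand as missing from the plan. If the sections on surveys, follow-up, withdrawal or data collection did restrict the survey to those with 3 months of use, the question of bias would have to be looked at again.
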